Belun Technology Company has conducted two studies in 2017-2018 and has published an abstract of their preliminary findings from Hong Kong at the 2018 APSS meeting. This validation study was conducted in Prince of Wales Hospital in Hong Kong using the original version of the Belun Ring which had no capability of detecting total sleep time (TST). This study excluded patients with a history of congestive heart failure (CHF), stroke, chronic obstructive pulmonary disease (COPD), neuromuscular disorder, or hypoventilation well as those on beta-blockers and calcium blockers. In-lab polysomnography (PSG) signals were recorded simultaneously with device under test and the reference apnea-hypopnea index (AHI) values were manually scored by certified sleep technician according to the American Academy of Sleep Medicine (AASM) Manual for the scoring of Sleep and Associated Events version 2.3. A total of 23 Chinese subjects (17 males, 6 females; 53.2 ± 11.8 years old) were enrolled in the validation and each subject contributed one record of overnight measurement. The time of sleep period was 352.1 ± 47.5 minutes and the distribution of the reference apnea-hypopnea index (AHI) was from 4.1 to 98.3 (38.5 ± 28.3) /hour. The correlation between reference apnea-hypopnea index (AHI) and Sleep Score is r = 0.977 (P<0.001). It was concluded that the overall sensitivity and specificity for the classification of severity of obstructive sleep apnea (OSA) are good, especially in moderate and severe groups. In the subsequent Colorado study (unpublished data), a newer version of Belun Ring with the capability of measuring total sleep time (TST) was used. The correlation between reference PSG-AHI and Belun Ring REI is r = 0.865 using an AHI cutoff of 15 and the overall accuracy was 84.4% with a sensitivity of 80% and a specificity of 88%. The Belun Ring-estimated total sleep time (TST) correlates well with the polysomnography (PSG)-derived total sleep time (TST) with an r = 0.950. In this study, the new version Belun Ring pulse oximeter will be used for evaluation which will be compared with the standard attended in-lab PSG in order to determine the accuracy, sensitivity, and specificity of Belun Ring as an outpatient evaluation for obstructive sleep apnea (OSA).

1 13

usion and Exclusion Criteria
Inclusion Criteria
All adult patients age 18-80 years old scheduled for overnight in-lab sleep study
Provision of signed and dated informed consent form
Exclusion Criteria

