Recent hospitalization in the past 30 days
Patients on home oxygen, non-invasive ventilator, diaphragmatic pacing, or any
form of nerve stimulator
Patients with pacemaker, defibrillator, left ventricular assist device (LVAD), or
status post cardiac transplantation
Patients with baseline heart rate under 50 bpm or over 100 bpm during last clinic
visit or prior to study at the sleep lab
Patients with unstable cardiopulmonary status judged to be unsafe for sleep study
by the sleep tech and/or the on-call sleep physician in the sleep lab on the night of
the study

- 6. Patients who are unable to complete the required study
- 7. *Patients involved in another investigational study*
- 8. Pregnant women

Number of Research Participants

We will enroll at least 80 subjects in two UH sleep laboratories.

Vulnerable Populations

- 1. Indicate specifically if you will include each of the following special populations by checking the appropriate box:
 - □ Adults unable to consent
 - □ Minors (infants, children, teenagers)
 - \Box Wards of the state
 - □ Foster Children
 - Pregnant Women
 - □ Neonates
 - □ Neonates of Uncertain Viability
 - ⊠ Employees of CWRU or UHHS
 - □ Prisoners
 - ⊠ Illiterate Individuals
 - \boxtimes Non-English Speaking
 - ⊠ University Students
 - □ None
- 2. If excluding pregnant women, illiterate or non-English speaking individuals, provide a scientific rationale for the exclusion. Inconvenience or cost is not an acceptable rationale. *There is unknown risks and benefits of the device to the growing fetus; hence pregnant women are excluded in this study.*
- 3. If the research involves individuals that are included in a vulnerable population, describe the additional safeguards included to protect the rights and welfare of the individuals for each population indicated.

The illiterate individuals are not excluded as long as they make a mark or able to sign their name in the written informed consent form. Also, the written informed consent form will be read to them verbatim before they give their consent.

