 - \boxtimes Medical record number
 - □ Health plan beneficiary number
 - □ Account number
 - □ Certificate/license number
 - \Box Any vehicle or other device serial
 - □ Device identifiers or serial numbers
 - \Box Web URL
 - □ Internet protocol (IP) address
 - \Box Finger or voice prints
 - □ Photographic images
 - Other: *Sleep study recording data*
- 2. List all other data to be collected for the research study (e.g. laboratory values, physician notes, length of stay, etc.)
 - a. Age, gender, race, weight, height, and BMI
 - b. Past medical and surgical histories
 - c. Concomitant medications
 - d. Physicians' notes on clinic visits for chart review to check subject eligibility

WESTERN	University	Sparta IRB	HRP-503BIO	TEMPLATE: Biom	edical Protocol	
RESERVE	Hospitals	Research Tracking + Administration	Approved:		Prior Version:	08/16/2018

- e. Previous polysomnography (PSG) and home sleep apnea test (HST) in the past
- *f.* All subjective information related to current sleep problem including current CPAP use
- g. SP21256 Sleep Questionnaire
- h. STOP-BANG score
- *i.* UH Pre-sleep Questionnaire part of routine care prior doing the standard polysomnography (PSG)
- *j.* UH Post-Sleep Questionnaire part of routine care after doing the standard polysomnography (PSG)
- *k.* Patient satisfaction survey part of routine care after doing the standard polysomnography (PSG)
- *l.* Arterial blood gas and bicarbonate values if available
- m. Echocardiogram or cardiac MRI results if needed
- n. Total sleep time, Sleep latency, SpO2 nadir, oxygen desaturation index (ODI) and overall apnea-hypopnea index (AHI) in the polysomnography (PSG) during the testing
- o. Total sleep time, SpO2 nadir, and respiratory event index (REI) in the Belun Ring device during the testing

Data Analysis Plan

RStudio Version 1.1.456 will be used to perform an a priori power analysis for the sensitivity of the Belun Ring REI and PSG AHI diagnoses. At alpha = 0.05, power = 0.95, minimum acceptable sensitivity = 0.825, target level of sensitivity = 0.977, a minimum of 35 obstructive sleep apnea (OSA)-positive patients is required. With an estimated 80% of patients receiving a positive polysomnography (PSG) diagnosis of obstructive sleep apnea, recruitment of 42 patients at minimum is necessary. Because not all recruited patients may complete the overnight PSG, we plan to collect data from approximately 50 patients.

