Sensitivity (the proportion of patients correctly diagnosed with OSA) and specificity (the proportion of patients correctly rejected as having OSA) values of sleep scores will be computed, and the area under the receiving operating characteristic (ROC) curve will also be calculated. A sensitivity value of .825 will be considered clinically significant. Pearson correlation will be used to identify the association between OSA and PSG AHI diagnoses. Bland and Altman plots will be generated to demonstrate the degree of identity between the outcomes of the Belun Rung and PSG AHI diagnostic methods.

Additional data such as sleep parameters, stress parameters, and total sleep time will be reported as descriptive analyses (e.g., means and standard deviations).

The primary study endpoint is to investigate the accuracy, sensitivity, and specificity of the Belun Ring in assessing obstructive sleep apnea (OSA) when compared to the gold standard which is polysomnography (PSG). The secondary endpoint is to evaluate the tolerability of the device by the patients.

Confidentiality of Specimens and Banking

Are you storing the specimen(s) for future use for other research projects?

- I am not collecting specimens in this research project
- I am **not** storing specimens in this research project
- □ Yes
- 🛛 No

Confidentiality of Data

- 1. To maintain the confidentiality of the data:
- ☑ I will use a unique study identifier (not derived from the participants' personal identifiers) to code individuals' data and I will store this ID log separate from study data.
- □ Other *(please explain)*:
- 2. How are you storing your electronic data?
 - ⊠ UH Redcap
 - □ CWRU Redcap
 - CWRU's SRE (Secure Research Environment)
 - □ CWRU Box
 - \Box OnCore
 - □ UH Secure Network Drive
 - □ CWRU Secure Network Drive

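### The only sensitivity criterion is an observed value of 0.825, the null of the power calculation; as written, a device truly at 0.825 meets it about half the time, not 5%

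*Combined protocol and SAP*

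**What the plan says.** The power paragraph of the Data Analysis Plan gives "At alpha = 0.05, power = 0.95, minimum acceptable sensitivity = 0.825", a target sensitivity of 0.977 and a minimum of 35 OSA-positive patients. It expects 80% of patients to be positive on polysomnography. From that it derives a minimum recruitment of 42 and adds that "we plan to collect data from approximately 50 patients". The Number of Research Participants section instead says "We will enroll at least 80 subjects in two UH sleep laboratories".

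The next paragraph of the Data Analysis Plan says that sensitivity and specificity will be calculated, along with the area under the ROC curve, a Pearson correlation and Bland–Altman plots. The only benchmark is "A sensitivity value of .825 will be considered clinically significant". The endpoint sentence reads "The primary study endpoint is to investigate the accuracy, sensitivity, and specificity of the Belun Ring". No section gives a hypothesis test, p-value, confidence interval or lower bound for sensitivity. The hypothesis under Objectives and the statement of benefit to society speak of a sensitive and specific device without a number.

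**The concern.** The same number has two incompatible jobs. In the power calculation 0.825 is the null value, the sensitivity that the study must show the device exceeds. In the results paragraph, reaching that value is enough. An estimate of sensitivity falls on either side of its true value about equally often, so a criterion placed at the null is met about half the time when the null is true.

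Sensitivity is the only part of the three-part primary endpoint for which the study is powered, and 0.825 is its only benchmark. If the sentence is applied as it stands, a device at or below the plan's own minimum could readily be reported as clinically significant, and the stated alpha and power would not describe the criterion used. The protocol envisages use as an alternative to in-laboratory polysomnography or as a screening tool before it. In either role, low sensitivity means missed disease.

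**Working it through.** **Inputs, all from the Data Analysis Plan unless noted.** Null sensitivity p0 = 0.825; target p1 = 0.977; alpha 0.05, sidedness not stated; power 0.95; 35 positives required; 80% expected positive. Expected positives: 42 × 0.80 = 33.6 (taken as 34), 50 × 0.80 = 40, and 80 × 0.80 = 64, the last using the enrolment figure from Number of Research Participants.

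**Step 1: reproduce the 35.** Arcsine formula: n = [(z_alpha + z_power) / (2·arcsin√p1 − 2·arcsin√p0)]². The denominator is 2.8371 − 2.2784 = 0.5587.
- One-sided alpha 0.05: [(1.645 + 1.645) / 0.5587]² = 34.7, so 35.
- Two-sided alpha 0.05: [(1.960 + 1.645) / 0.5587]² = 41.6, so 42.

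The stated 35 is therefore a one-sided 5% test of 0.825. The exact binomial test agrees: at 35 positives it needs 33 detected, with type I error 4.2% and power 95.4%.

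**Step 2: error rate of the criterion as written.** With n positives, the criterion is met when the number detected X is at least r, the smallest integer not below 0.825n. The pass probability is P(X ≥ r), with X binomial (n, true sensitivity). The last column is the exact (Clopper–Pearson) one-sided 95% lower bound for the smallest passing result.

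| Positives n | Smallest passing result | Pass probability, truth 0.825 | Pass probability, truth 0.80 | Lower bound |
|---|---|---|---|---|
| 34 | 29/34 | 43.9% | 30.0% | 0.715 |
| 35 | 29/35 | 58.5% | 43.3% | 0.689 |
| 40 | 33/40 | 59.9% | 43.7% | 0.696 |
| 64 | 53/64 | 55.3% | 35.2% | 0.732 |

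Over every count from 30 to 80 positives, the pass probability at 0.825 runs from 43.9% (n = 34) to 59.9% (n = 40), and it is below 50% at 19 of the 51 counts. Letting the number of positives vary as binomial (N, 0.80), it averages 51.5%, 53.0% and 51.8% for N = 42, 50 and 80. At a true 0.80 the averages are 37.0%, 37.1% and 32.2%.

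**Step 3: the rule that the stated alpha implies.** Choose the smallest c with P(X ≥ c) ≤ 0.05 at 0.825. This is the same as requiring the exact one-sided 95% lower bound to exceed 0.825.

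| Positives n | Pass mark | Type I error | Power at 0.977 | Pass probability, truth 0.80 |
|---|---|---|---|---|
| 35 | 33/35 (94.3%) | 4.2% | 95.4% | 1.9% |
| 40 | 38/40 (95.0%) | 2.0% | 93.6% | 0.8% |
| 64 | 59/64 (92.2%) | 2.3% | 99.6% | 0.7% |

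With 40 positives, 33 detected meets the sentence as written, while the stated alpha calls for 38.

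**The case against.** The strongest reply is that the plan never says the criterion applies to the point estimate. It says clinically, not statistically, significant, and the power paragraph calls the same number a minimum acceptable value. On that reading 0.825 is the threshold a test must exclude, and the test was simply not written out. That may be what the authors meant. But a reader following the text has no such test to apply, and the two readings put the pass mark at about 83% or at 92–95%. The 44–60% figure is conditional on the literal reading; the absence of a stated rule is not.

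Several smaller points have some force:
- The 44% end of the range comes from 34 positives, one below the required 35, and reflects binomial discreteness. About one half is the fairer summary.
- No treatment or stopping decision depends on the result, so the harm is an over-favourable conclusion rather than a risk to participants.
- The exact bound is conservative, with actual error near 2% at 40 and 64 positives. Another prespecified interval method could serve.
- A proper rule is harder to pass. At a true sensitivity of 0.90 it is met only 31%, 22% and 37% of the time at 35, 40 and 64 positives. With only the 42-patient minimum, average power at 0.977 is 89.8%.
- The earlier study of a newer ring version in Background reports 80% sensitivity at an AHI cutoff of 15. The analysis plan states no cutoff, so that figure is only indicative.

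None of these supplies the missing link between 0.825 and alpha 0.05.

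**Conclusion.** The concern holds. The plan's only sensitivity criterion sits on the null of its own power calculation and has no test or bound attached. Applied as written, it passes a device at the minimum acceptable sensitivity about half the time, roughly ten times the stated 5%. The conclusion does not depend on whether 42, 50 or 80 patients are enrolled.

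It rests on three assumptions: the sentence is applied to the observed proportion, detections are independent between patients, and about 80% of patients are positive, as the plan expects. The prevalence assumption matters little, since the pass probability stays between 43.9% and 59.9% at every count from 30 to 80 positives. The 5% comparator takes alpha as one-sided, which is what reproduces 35. If alpha were two-sided, the relevant tail would be 2.5% and the gap wider.

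**What to change.** Replace the criterion sentence with: *The sensitivity criterion is met if the exact (Clopper–Pearson) one-sided 95% lower confidence bound for sensitivity exceeds 0.825.* State that alpha 0.05 is one-sided. Report two-sided 95% exact intervals for sensitivity, specificity and accuracy. Restate power for the number of positives actually planned. The exact bound is suggested because it holds the error at or below 5% at every count. If another method is preferred, name it and its sidedness before the data are analysed.

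The cost is one sentence and no additional data, plus a higher pass mark: 33/35, 38/40 or 59/64 in place of 29/35, 33/40 or 53/64. From 35 positives up, power at 0.977 falls below the planned 0.95 only at 37 to 41 positives (93.2–94.7%). Averaged over a random number of positives it is 95.2% with 50 patients and 99.8% with 80, but 89.8% with 42, so the 42-patient minimum would not deliver the stated power. At 40 and 64 positives the pass mark is the same at one-sided 0.05 and 0.025, so the choice of sidedness costs nothing there.
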